#### 4.1.1 DOSE ESCALATION

For all cohorts, a sentinel group of 2 participants (1 assigned to XTMAB-16 and 1 assigned to placebo) will be dosed at least 48 hours before the remaining participants in the same cohort. After blinded review of the available safety and laboratory data by the PI, if no notable safety signals are identified, the remaining participants within the same cohort will be dosed.

Participants within a cohort should be dosed at least 1 hour apart.

As XTMAB-16 is a TNF $\alpha$  inhibitor, which have well-characterized clinical safety profiles, it can be given to participants in the 4 mg/kg dose group after 14 to 21 days clinical assessment of the participants at 2 mg/kg dose group, unless safety concerns arise.

Dose escalation will be stopped as soon as safety signals or risks are identified or anticipated, based on:

- Number of abnormal and clinically significant safety laboratory results
- Number of SAEs and/or TEAEs with severity/intensity high enough for a meaningful decision
- Proportion of TEAEs of the same type high enough to justify the decision

The severity rating is adapted to healthy participants, taking into account event characteristics such as type, deleterious potential, occurrence, progression, and monitorability. A solitary SAE occurrence is not by itself a criterion for making a decision (assessment depends on the nature of the reported event). See Section 4.1.2 for details on stopping rules.

A decision to proceed from dose “n” to the next higher “n+1” dose will be made jointly by the Sponsor and the Investigator based on a preliminary Investigator blinded safety report inclusive of the 12 participants in dose level cohort “n”. The relevant data for this decision should be, at a minimum, AEs, liver and kidney function tests, ECG, blood pressure, and heart rate.

For safety purposes, the treatment of a specific participant may be unblinded before the next dose level is administered, after mutual agreement between the Sponsor and the Investigator.

An unscheduled PK sample collection and analysis may be performed to support the clinical safety assessment, if needed in the event of a safety signal of concern.

Depending on the tolerability profile and safety laboratory results observed in the dose level cohort “n,” one of the following decisions will be made for cohort “n+1”:

- Dose escalation may continue as scheduled.

- A higher intermediate dose between the current dose (“n”) and the next planned dose (“n+1”) may be administered to the next cohort.
- A lower intermediate dose between the current dose (“n”) and the previous dose (“n-1”) may be administered to the next cohort, including the possibility of administering a dose lower than the starting dose.
- The study may be stopped.

---

#### 4.1.2 STOPPING RULES

##### 4.1.2.1 CRITERIA

Participants who experience injection site reactions or vital signs changes of Grade 1 or 2 (see [Appendix 4](#)) during infusion may continue infusion or have infusion interrupted for treatment and then resumed, at the discretion of the Investigator. Participants who experience injection site reactions or vital signs changes of Grade 3 or 4 during infusion should have infusion terminated and will be treated, as needed, for the adverse events. Any participant who experiences anaphylaxis during infusion will have infusion terminated; diagnosis of and recommended treatment for anaphylaxis is provided in [Appendix 5](#).

In addition to the assessment of SAEs and the occurrence/severity of other AEs by the Sponsor and the Investigator, after exploring potential confounding factors, the following criteria should be considered as guidance for the decision to stop dose escalation or to stop administration of the study drug to additional participants:

- 1 SAE for which the relationship to treatment cannot be reasonably excluded
- 1 AE of severe intensity for which the relationship to treatment cannot be reasonably excluded
- 3 or more participants with AEs of moderate intensity for which the relationship to treatment cannot be reasonably excluded
- 1 participant in a cohort with potential Hy's Law values
  - ALT or AST  $>8 \times$  upper limit of normal (ULN)
  - ALT or AST  $>5 \times$  ULN for more than 2 weeks
  - ALT or AST  $>3 \times$  ULN and (total bilirubin  $>2 \times$  ULN or INR  $>1.5$ )
  - ALT or AST  $>3 \times$  ULN with the appearance of fatigue, nausea, vomiting, right upper quadrant pain or tenderness, fever, rash, and/or eosinophilia ( $>5\%$ )
- QTcF  $\geq 500$  ms (men and women)
- Any other clinically significant intolerance findings

If any of the above occur, the Contract Research Organization (CRO) and Sponsor should be notified within 24 hours of becoming aware of the event. Decisions to stop dose escalation or stop administration of study drug to additional participants will be determined collectively between the PI, CRO Medical Monitor, and Sponsor.

#### 4.1.2.2 ACTIONS

At each dose level, if 1 of the above criteria is met at that dose level, the treatment blind will be broken by the Sponsor for the concerned participants as follows:

- If 3 or more participants were given XTMAB-16 and no participant was given placebo, drug administration will be stopped for these participants and all other participants in that dose level; and either
  - One or more lower dose(s) may be considered, only if, after reviewing all data, the Investigator and the Sponsor agree that it is safe to do so, or
  - Study may be stopped.
- Otherwise, drug administration per protocol may either continue as planned or be reconsidered if, after reviewing all data, the Sponsor and the Investigator agree that it is safe to do so; and either
  - The current dose level may be continued, or
  - One or more lower dose(s) may be considered, or
  - The study may be stopped

The drug administration per protocol may either continue as planned or be reconsidered only if, after reviewing all data, the Sponsor and the Investigator agree that it is safe to do so.

The treatment blind may be broken for other reasons, supported by a clear rationale.

The Investigator and Sponsor may decide to stop study drug administration based on other safety signals not described in the above criteria.

## 4.2 SCIENTIFIC RATIONALE FOR STUDY DESIGN

The design of this Phase 1, SAD clinical trial is similar to other FIH studies evaluating TNF $\alpha$  inhibitors.

Based on TK results in the 6-week, GLP, toxicology study in hTNF $\alpha$  transgenic (TgTC) mice, the half-life ( $t_{1/2}$ ) of XTMAB-16 ranged from 9.4 days (226.9 hr) at 10 mg/kg to 13.6 days (327.2 hr) at 40 mg/kg, which is comparable to the half-life of 10 mg/kg of infliximab in humans of 13.9 days (335.1 hr). Approximately 90% of XTMAB-16 after a single dosing is expected to be eliminated from the system in 8 weeks. Therefore, the 8-week study duration is considered adequate to support safety and PK, biomarker, and immunogenicity analyses.

In support of the effect of XTMAB-16 on TNF $\alpha$ , additional biomarkers associated with TNF $\alpha$  activity and sarcoidosis have been selected for investigation in this first-in-human (FIH) study. The biomarkers selected for this study are sIL-2R, ACE, TNF $\alpha$ , and IL-6. ACE is a common biomarker used in the diagnosis of sarcoidosis. sIL-2R is a surrogate marker for T cell activation, is significantly elevated in sarcoidosis patients, and has been shown to have a high and superior sensitivity and specificity, compared to ACE, for diagnosing sarcoidosis in patients. IL-6 is elevated in patients with sarcoidosis and may be involved in the initiation and maintenance of alveolitis by activating and causing the proliferation of T cells. TNF $\alpha$  induces IL-6 through the nuclear factor k B pathway and, thus, inhibition of TNF $\alpha$  through XTMAB-16 is likely to be reflected in a change in IL-6 circulating levels. These biomarkers are normally low or undetectable in healthy participants. However, as XTMAB-16 is intended for use in patients with pulmonary sarcoidosis (in whom these biomarkers are likely to be elevated), XTMAB-16 is expected to influence the levels of these biomarkers in patients. Measuring these biomarkers in healthy participants will establish relative baseline levels of these biomarkers for comparison in later trials in patients.

#### 4.3 JUSTIFICATION FOR DOSE

The participants in this study will receive a single IV infusion of placebo or 2 or 4 mg/kg of XTMAB-16 in 250 mL of 0.9% Sodium Chloride Injection, US Pharmacopeia (USP).

Based on the clinical data from literature in sarcoidosis patients with pulmonary involvement, and safety data from the mouse toxicology study, the low doses of 2 to 4 mg/kg of XTMAB-16 in the current study are considered safe and expected to be relevant for PK and efficacy biomarker analyses to support further clinical development. Using mg/kg scaling from the 40 mg/kg TgTC mouse NOAEL in the 13-wk toxicology study, the 2 and 4 mg/kg human dose cohorts provide a 5 and 10-fold safety margin respectively.

Projected human safety margins were calculated by comparing the NOAEL exposure in the toxicology species (TgTC mice dosed at 40 mg/kg) to the projected clinical exposures. Using TK data generated from the 6-week GLP toxicology study in TgTC mice, a 2-compartmental model with first order absorption and elimination using a mixed ratio error model was developed for XT-MAB16. The model was allometrically scaled to humans using published allometric exponents. The allometrically scaled human model was then used to simulate the planned FIH doses for XTMAB-16 for a 70 kg human (Table 3).

The projected human doses were then compared to the calculated  $C_{max}$  and  $AUC_{0-\infty}$  from the 13-week NOAEL to generate exposure based safety margins (Table 3). Using a model built from

the 6-week toxicology study Comparing the  $AUC_{0-\infty}$  (624865.9 hr•mg/mL) of the 40 mg/kg group dosed with XT-MAB16 in TgTC model toxicology study to the estimated  $AUC_{0-\infty}$  of the 2 mg/kg dose in humans (14000 hr•mg/mL) the safety margin for the starting dose is approximately 89-fold. Comparing the  $C_{max}$  (1104.9 mg/mL) of 40 mg/kg dose of XTMAB-16 in TgTC to the estimated  $C_{max}$  (47.8 mg/mL) of 2 mg/kg dose in humans, the safety margin for the starting dose is approximately 23-fold.

In the repeat-dose 13-week toxicology study, the animals received 7 biweekly IV injections (Day 1, 15 and 29), while in the current study, only a single IV infusion will be administered to the human subjects.

Therefore, the single administered doses of 2 and 4 mg/kg in the planned FIH study are considered scientifically reasonable and meet current guidance for Maximum Safe Starting Dose 2005 and appropriate safety margins for both the starting and highest dose based on the NOAEL exposure reported in the 13-week GLP TgTC toxicology study.

The relevant human projected safety margins calculated from the 13-week toxicology study are summarized in [Table 3](#) below.

**Table 3** Allometrically Scaled Estimated Human PK Parameters

PK Parameter	2 mg/kg	4 mg/kg
$C_{max}$ (μg/mL) Mean	47.8	95.7
Safety Margin for $C_{max}$	23	12
$AUC_{0-\infty}$ (μg/mL•hr) Mean	14000	28000
Safety margin for $AUC_{0-\infty}$	45	22

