### 2.2.4 TOXICOLOGY OVERVIEW

The 6-week GLP, TgTC mouse, toxicology study included: (1) a main (toxicity) study (60 animals, 10 /sex/dose; vehicle vs 20 mg/kg vs 40 mg/kg), with a 4-week treatment period followed by a 2-week recovery period, to evaluate the toxicity of KBMAB-16 (clinical drug product XTMAB-16) from 3 biweekly IV injections (Days 1, 15, 29); and, (2) a satellite (toxicokinetic [TK]) study

(132 animals, 2/sex/dose/time point for 10 time points) to characterize a single IV dose TK profile. The findings are summarized below.

KBMAB-16 was well tolerated up to 40 mg/kg after 3 biweekly IV injections. All animals survived in the toxicity study with no meaningful abnormal clinical and pathological findings. Thus, the no adverse effect level (NOAEL) of KBMAB-16/XTMAB-16 was considered to be 40 mg/kg via 3 biweekly IV injections in TgTC mice.

In the TK groups, a complete 6-week (1008 hours) TK profile following a single dose (10 mg/kg, 20 mg/kg and 40 mg/kg) of KBMAB-16 was obtained. After a single 40 mg/kg IV injection, the maximum observed concentration ( $C_{max}$ ) was at 791.0  $\mu$ g/mL and the area under the concentration-time curve ( $AUC_{0-\infty}$ ) was at 124257.2  $\mu$ g\*hr/mL. The systemic exposure in terms of  $C_{max}$  and  $AUC_{0-\infty}$  were increased proportionally in the dose range from 10 to 40 mg/kg of KBMAB-16. The half-life ( $t_{1/2}$ ) of XTMAB-16 ranged from 9.4 days (226.9 hr) at 10 mg/kg to 13.6 days (327.2 hr) at 40 mg/kg, which is comparable to the half-life of 10 mg/kg of infliximab in humans of 13.9 days (335.1 hr).

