In a 13-week, repeated dose, GLP, toxicology study (Study 14042-20005) in hTNF $\alpha$  transgenic mice, KBMAB-16 was well tolerated up to 40 mg/kg after 7 bi-weekly IV injections in TgTC animals in the toxicity study with no meaningful test article related clinical and pathological abnormalities observed. The NOAEL of KBMAB-16 was considered to be 40 mg/kg after 7 doses biweekly IV injection in TgTC mice. In addition, safety pharmacology assessments of the central nervous system (CNS) and respiratory systems did not reveal adverse effects at any dose of KBMAB-16. After 40 mg/kg IV injection for 6 doses, the  $C_{max}$  was 1104.9  $\mu$ g/mL, the  $(AUC)_{0-\infty}$  was 624865.9  $\mu$ g\*hr/mL and the  $(AUC)_{0-\tau}$  was 124878.7  $\mu$ g\*hr/mL. The systemic exposure in terms of  $C_{max}$  and  $(AUC)_{0-\infty}$  increased in a dose proportional manner in the dose range from 10 to 40 mg/kg of KBMAB-16.

For further detailed nonclinical data for XTMAB-16, refer to the IB.

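### The AUC safety margins of 45 and 22 set a repeat-dose mouse exposure against a single human dose; on the protocol's own per-interval or single-dose figures they are about 9 and 4.5

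*Protocol*

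**What the plan says.** Protocol Section 2.2.4 reports two mouse studies that both reached 40 mg/kg.

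- **6-week study, toxicokinetic groups.** "After a single 40 mg/kg IV injection, the maximum observed concentration" was 791.0 µg/mL, and AUC0-inf "was at 124257.2" µg·hr/mL. Half-life ran from 9.4 days at 10 mg/kg to 13.6 days at 40 mg/kg.
- **13-week study.** The no-adverse-effect level was set at 40 mg/kg after "7 bi-weekly IV injections in TgTC animals". The exposure figures are introduced by "After 40 mg/kg IV injection for 6 doses": Cmax 1104.9 µg/mL, AUC0-inf 624865.9 and AUC0-tau 124878.7 µg·hr/mL.

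Section 4.3 projects human exposure from a model built on the 6-week toxicokinetic data. It then takes Cmax and AUC0-inf "from the 13-week NOAEL to generate exposure based safety margins". Table 3 gives projected human AUC0-inf of 14000 and 28000 µg·hr/mL with margins of 45 and 22, and Cmax margins of 23 and 12. The text says that the animals had repeated injections whereas "only a single IV infusion will be administered to the human subjects", but it makes no adjustment to the AUC margin. It closes by finding "appropriate safety margins for both the starting and highest dose based on the NOAEL exposure reported in the 13-week GLP TgTC toxicology study".

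The text of Section 4.3 also gives an AUC margin of about 89-fold for 2 mg/kg, and margins by mg/kg scaling of 5-fold at 2 mg/kg and 10-fold at 4 mg/kg.

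**The concern.** An exposure margin is a ratio, so its numerator and denominator should describe the same kind of exposure. Here the denominator is the whole exposure from one human infusion, projected from single-dose mouse data. The numerator is an AUC to infinity reported after six doses, so it includes drug from more than one dose. The protocol already holds two figures at the same mouse dose that sit closer to one human dose, and the margin uses neither.

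The AUC margin is one of the stated grounds for both dose levels in a first-in-human study. Someone who takes 45 and 22 from Table 3, or 89 from the text, would think exposure lies much further below the no-adverse-effect level than the comparable figures show.

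**Working it through.** **Inputs.** From Protocol Section 2.2.4, mouse at 40 mg/kg: AUC0-inf 624865.9 (13-week study, after six doses), AUC0-tau 124878.7 (13-week study), AUC0-inf 124257.2 (6-week study, single dose), Cmax 1104.9 and 791.0. From Section 4.3, Table 3, projected human: AUC0-inf 14000 and 28000, Cmax 47.8 and 95.7.

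**Formula.** Margin = mouse exposure / projected human exposure.

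**1. The plan's own figures.**
- AUC: 624865.9/14000 = 44.6 and 624865.9/28000 = 22.3, which round to 45 and 22.
- Cmax: 1104.9/47.8 = 23.1 and 1104.9/95.7 = 11.5, as tabulated.

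Table 3 therefore reproduces.

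**2. AUC margins on the other bases in the protocol.**

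| Mouse exposure | 2 mg/kg | 4 mg/kg |
|---|---|---|
| AUC0-inf after six doses, 624865.9 | 44.6 | 22.3 |
| AUC0-tau, 124878.7 | 8.92 | 4.46 |
| Single-dose AUC0-inf, 124257.2 | 8.88 | 4.44 |

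The last two numerators agree within 0.5% (124878.7/124257.2 = 1.005), as linear kinetics near steady state would predict. The tabulated margins are larger by 624865.9/124878.7 = 5.00 and 624865.9/124257.2 = 5.03.

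**3. Cross-check per mg/kg.** Projected human AUC per mg/kg is 14000/2 = 7000. The single-dose mouse value is 124257.2/40 = 3106. The human value is 7000/3106 = 2.25 times the mouse value, so the dose ratio 40/2 = 20 becomes 20/2.25 = 8.9. A margin of 45, above the dose ratio of 20, arises only with the repeat-dose numerator.

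**4. Other margins in the text of Section 4.3.**
- About 89-fold AUC margin at 2 mg/kg: the inputs named there are 624865.9 and 14000, which give 44.6. Reaching 89 needs a human AUC of 624865.9/89 = 7021, about half the projected value.
- mg/kg scaling, stated as 5 and 10: 40/2 = 20 and 40/4 = 10.

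**5. What 624865.9 measures (a query).** Section 2.2.4 does not say whether its time zero is the sixth dose or the first.
- *From the sixth dose.* Assume a 14-day interval, one-exponential decline and the half-lives of the 6-week study. Then AUC0-inf/AUC0-tau = 1/(1 − 2^(−14/t½)), which is 1.55 at 9.4 days and 1.96 at 13.6 days. The reported ratio is 5.00, which would need t½ = 14 × ln 2 / [−ln(1 − 1/5.004)] = 43.5 days. With ratios of 1.55 to 1.96, the margins would be 124878.7 × 1.55/14000 = 13.8 to 124878.7 × 1.96/14000 = 17.5 at 2 mg/kg, and 6.9 to 8.7 at 4 mg/kg.
- *Over the whole course.* Six single-dose AUCs sum to 6 × 124257.2 = 745543. The reported figure is 624865.9/745543 = 84% of that, so the same order of magnitude. It would then be a cumulative exposure from several doses.

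**The case against.** The strongest reply is that the section says what it does. It names the 13-week AUC0-inf, Section 2.2.4 gives the number of doses, and Section 4.3 itself contrasts repeated dosing in mice with one infusion in humans. The no-adverse-effect level was set after repeated dosing, so a repeat-dose exposure is a defensible anchor. The single-dose AUC comes from a different study. AUC0-tau is truncated at one interval and matches a single-dose AUC0-inf only under linear kinetics near steady state. Dose levels and justification were revised at the regulator's request, and the section also cites clinical literature, mg/kg scaling and Cmax.

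Much of this stands. The current figure need not be removed, and choosing AUC0-tau or the single-dose AUC as comparator involves judgment. The reply does not answer the main point: neither reading of 624865.9 makes it the counterpart of one human dose, and the section shows no margin on a basis that is.

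A reader might also infer three stronger claims that the documents do not support:

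- **That Table 3 is miscalculated.** It is not; the fault lies in the exposure basis.
- **That 624865.9 is wrong because it conflicts with the half-life.** The conflict exists only if time zero is the sixth dose. It also borrows half-lives from the 6-week study and assumes one-exponential decline. The protocol gives no half-life for the 13-week study and refers to the Investigator's Brochure for detail.
- **That 45 is the section's most favourable AUC margin.** The text states about 89-fold.

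**Conclusion.** The point holds as one of comparability and internal consistency. On the protocol's own per-interval or single-dose exposures the AUC margins are 8.9 at 2 mg/kg and 4.4 to 4.5 at 4 mg/kg, one fifth of the 45 and 22 in Table 3 and one tenth of the 89 in the text. These ratios need only the stated figures. Treating AUC0-tau as equivalent to a single-dose AUC0-inf assumes linear kinetics near steady state, which the 0.5% agreement supports. Two further contradictions need no assumptions: 89 against 44.6 from the same inputs, and 5 against 20 for the mg/kg margin at 2 mg/kg, an error in the unfavourable direction. The meaning of 624865.9 remains a question for the sponsor.

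A reader might go on to infer that either dose is unsafe. The documents do not show that: every restated margin exceeds 1 and the Cmax margins of 23 and 12 reproduce. The Cmax margins also use the repeat-dose study; with the single-dose Cmax they would be 791.0/47.8 = 16.5 and 791.0/95.7 = 8.3. No endpoint, analysis set or planned analysis is affected.

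**What to change.** In Protocol Sections 2.2.4 and 4.3:

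1. Verify 624865.9 against the 13-week study report and state its time zero. If it runs from the sixth dose, explain the ratio of 5.0 to AUC0-tau. If it covers the whole course, label it cumulative.
2. Add to Table 3 the AUC margins on the per-interval basis (8.9 and 4.5), the single-dose basis (8.9 and 4.4), or both, beside the current 45 and 22. Say which basis the dose justification rests on.
3. Reconcile the 89-fold statement with Table 3, and the 5- and 10-fold statement with 40/2 and 40/4.

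The cost is one source check and a few edited figures. The downside is that the stated AUC margins become less favourable. Whether the dose rationale needs rewording is for the sponsor and investigator; no dose is proposed or judged here.

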#### 4.4 END OF STUDY DEFINITION

A participant is considered to have completed the study if he or she has completed all phases of the study including the last visit shown in the Schedule of Assessments (SoA), Section [1.3](#).

## 5 STUDY POPULATION

### 5.1 INCLUSION CRITERIA

Participants must meet all of the following criteria to be eligible for participation in this study:

1. In the opinion of the Investigator, the participant is capable of understanding and complying with protocol requirements.
2. The participant is willing to sign and date a written, informed consent form and any required privacy authorization prior to the initiation of any study procedures, including requesting that a participant fast for any laboratory evaluations.
3. The participant is a healthy adult male or female aged 18 to 45 years, inclusive, at the time of informed consent.
4. The participant weighs between 45 kg (99 lbs) and 100 kg (220 lbs) and has a body mass index (BMI) between 18.0 and 30.0 kg/m^2, inclusive, at the time of informed consent.
5. The participant has physical examination, clinical laboratory values, and ECG results that are clinically acceptable. Laboratory results outside of the reference range must be documented as acceptable by the Investigator and Sponsor.
6. A male participant who is nonsterilized and sexually active with a female partner of childbearing potential must agree to use highly effective contraception from the time of signing the informed consent throughout the duration of the study, and for 90 days after the last dose of study drug. See [Appendix 3](#) for details on contraception requirements during the study.
7. A female participant of childbearing potential who is sexually active with a nonsterilized male partner agrees to routinely use highly effective contraception from the time of signing the informed consent, throughout the duration of the study, and for 90 days after the last dose of study drug. See [Appendix 3](#) for details on contraception requirements during the study.

